To achieve our long term goal of integrating lifestyle modifications to reduce cancer risk and related disparities for rural populations, understanding the underlying biological mechanism of weight loss, body composition, and inflammation is critical. However, empirical evidence documenting the efficacy of lifestyle weight loss interventions in rural populations is limited. Among completed or recently awarded trials (as of January 2020), none measured body composition and inflammation markers. Estimating the effect of lifestyle interventions on weight loss, body composition, and disease risk factors (inflammatory markers, lipid profiles) in rural populations is essential for the design and implementation of evidence-based approaches on a larger scale.

This study will recruit up to 50 obese rural Ohio residents and randomly assigned to a 15-week telephone-based weight loss (n=30) or an active control group (up to 20). The study objective is to determine the feasibility and preliminary efficacy of a 15-week telephone-based weight loss intervention on weight, body composition, and inflammatory markers, with tailored strategies and group messages to address barriers, self-efficacy, and social support for rural Ohio populations. We will utilize a novel and applicable point-of-care approach to assess body

composition, lipid profiles, and cancer risk factors in rural community settings. The Specific Aims for this study are:

1. To determine the feasibility and acceptability of a 15-week telephone-based weight loss intervention among obese rural residents.

We hypothesize that 80% of obese rural residents who participate in the study will complete the assigned intervention (**feasibility**), and 80% of the participants in the intervention group will engage in at least 75% of the weekly telephone counseling session (**acceptability**). During the 15-week weight loss intervention, we anticipate the minimal occurrence of intervention-related adverse events.

2. To estimate the preliminary efficacy of the lifestyle modifications on weight loss, body composition (fat mass, fat percentage), inflammatory biomarkers (IL-6, TNF- α , and CRP), and other disease risk factors (lipid profiles).

We hypothesize that the lifestyle intervention will result in substantial improvements in weight loss, fat mass, fat percentage, IL-6, TNF- α , CRP, and lipid profiles (with moderate effect size), compared to the active control group.

B BACKGROUND AND RATIONALE

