We considered using a standard measure of body composition using Dual-energy X-ray absorptiometry (DXA) but opted not to as this is likely to add the burden of travel to facilities equipped with DXA. However, we will assess body composition using a 3-D Styku body scanner, which is portable to rural community-settings and can provide valid and reliable data on body composition. Together with using Cholestech LDX to evaluate participants' lipid profiles, the proposed study is innovative to test new point-of-care approaches to assess disease risk factors in rural populations.

D DATA HANDLING AND ANALYSES

D.1. Outcome Analysis Plan

D.1.a Primary outcome

The feasibility of completing the study is defined as the percentage of enrolled participants who complete the study. If we observe an 80% completion rate in the weight loss intervention group (n=30), the 85%, 90%, and 95% confidence intervals (CIs) for the completion rate would be (69.5, 90.5), (68.0, 92.0), and (65.7, 94.3), respectively. If the true completion rate is 80%, we have 95% power to rule out the unacceptable 50% completion rate with 95% confidence (one-sided).

The acceptability of the weight loss intervention is the percentage of participants in the weight loss intervention group who engage at least 75% of the weekly telephone counseling session. Intervention-related adverse events, satisfactory, and other feasibility assessments, such as the percent of initial contact to enrollment, reasons for consent refusal, barriers to adherence to weekly goals, and reasons for drop-out will also be assessed.

D.1.b Secondary outcome

Significance test for the preliminary efficacy of the lifestyle intervention will quantify the difference in means using repeated measures analysis of variance (ANCOVA) statistical model to adjust baseline values and control for the effect of age. The sample size of 30 participants in the weight loss group and at least 15 in the active control group is feasible to recruit for a pilot/preliminary efficacy study that accounts for a projected attrition rate of 20% yet also still provides adequate power to detect meaningful, moderate to large effect size (0.54-0.72) on weight loss, body composition, inflammatory markers, and lipid profiles.

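### The completion-rate intervals in D.1.a are Wald intervals whose lower limits are about 2 to 4 points too favourable; the power figure beside them is approximate and conservative.

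*Combined protocol and SAP*

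**What the plan says.** Section D.1.a (Primary outcome) supposes a result: "If we observe an 80% completion rate in the weight loss intervention group (n=30"). For that result it lists two-sided 85%, 90% and 95% limits, in percent, as "69.5, 90.5), (68.0, 92.0), and (65.7, 94.3), respectively". It then gives a power statement. The assumption is "If the true completion rate is 80"%, and on that basis "we have 95% power to rule out the unacceptable 50% completion rate with 95% confidence (one-sided").

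The section does not name the interval method or the test, gives no number of completers at which 50% counts as ruled out, and does not say whether 95% is exact, rounded or a minimum.

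Section A.3 (Specific Aims) states the matching hypothesis, that "80% of obese rural residents who participate in the study will complete the assigned intervention".

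**The concern.** This paragraph is the only statement of power and precision for the primary outcome. For a feasibility claim the lower confidence limit matters most, because it says which poor completion rates the result excludes. With 30 participants and a rate near 80%, an interval that is symmetric about the observed proportion tends to sit too high. If the listed intervals are of that kind, the planned precision looks better than it is, and the final report may carry the same method forward.

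The power sentence also needed a check. Without a named test or cut-off, a reader cannot tell what 95% refers to or how many completers would meet the criterion.

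**Working it through.** **Inputs, all from D.1.a:** n = 30 (weight loss arm), observed proportion p = 0.80 (24/30), assumed true rate 0.80, unacceptable rate 0.50, one-sided 5% level.

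**1. Reproduce the stated intervals.** Wald: p ± z·√(p(1−p)/n), with √(0.8 × 0.2/30) = 0.0730.

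- 85%: 0.80 ± 1.440 × 0.0730 = 69.5 to 90.5
- 90%: 0.80 ± 1.645 × 0.0730 = 68.0 to 92.0
- 95%: 0.80 ± 1.960 × 0.0730 = 65.7 to 94.3

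All three match, so the arithmetic is right and the method is Wald.

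**2. Compare with better-behaved limits at 24/30.** Wilson: centre (p + z²/2n)/(1 + z²/n), half-width z·√(p(1−p)/n + z²/4n²)/(1 + z²/n). At 95% the centre is (0.8 + 0.0640)/1.1280 = 0.766 and the half-width is 1.96 × 0.0800/1.1280 = 0.139. Exact (Clopper-Pearson): the lower limit is the α/2 quantile of Beta(24, 7) and the upper limit the 1−α/2 quantile of Beta(25, 6).

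| Level | Wald (as stated) | Wilson | Exact | Wald lower minus Wilson | Wald lower minus exact |
|---|---|---|---|---|---|
| 85% | 69.5–90.5 | 67.7–88.4 | 66.1–89.9 | 1.8 | 3.4 |
| 90% | 68.0–92.0 | 65.7–89.3 | 64.3–90.9 | 2.2 | 3.7 |
| 95% | 65.7–94.3 | 62.7–90.5 | 61.4–92.3 | 3.0 | 4.3 |

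Differences are taken before rounding. The fault is mainly an upward shift: the 95% Wilson interval is slightly narrower than the Wald interval but sits lower.

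**3. Behaviour at the plan's own assumed rate.** With X ~ Binomial(30, 0.8):

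- 90% Wald. At 27/30 the lower limit is 0.90 − 1.645·√(0.9 × 0.1/30) = 0.810, above the true 0.80. P(X ≥ 27) = 0.0785 + 0.0337 + 0.0093 + 0.0012 = 12.3%, against a nominal 5%. The interval lies wholly below the truth for X ≤ 19, with probability 2.6%. Coverage is 100 − 12.3 − 2.6, or 85.2% before rounding.
- 90% Wilson or exact. The lower limit first exceeds 0.80 at 28/30. P(X ≥ 28) = 0.0337 + 0.0093 + 0.0012 = 4.4%.
- 85% Wald: coverage 81.6%.
- 95% Wald: coverage 94.6%, close to nominal, although the lower limit exceeds the truth 4.4% of the time against 2.5%.

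**4. Power against 50%, by exact binomial tails.**

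| Rule | Size at 50% | Power at 80% |
|---|---|---|
| ≥ 20/30 (one-sided 5%) | 4.94% | 97.4% |
| ≥ 21/30 (one-sided 2.5%) | 2.14% | 93.9% |

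Normal approximations, using √(0.25/30) = 0.0913:

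- one-sided 5%, null standard error throughout: Φ(0.30/0.0913 − 1.645) = Φ(1.641) = 95.0%
- one-sided 5%, null standard error for the critical value and alternative standard error for power: Φ((0.30 − 1.645 × 0.0913)/0.0730) = 98.0%
- the same formula with z = 1.96: 95.1%

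The stated 95% therefore reproduces in two ways, one of them at the level the plan states.

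**5. Effect on the decision about 50%.** At one-sided 5% the lower bound first exceeds 50% at 20/30 by every method: Wald 52.5%, Wilson 51.7%, exact 50.1%. At 19/30 all three are below 50%.

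**The case against.** The case for leaving the text alone has several parts.

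- **The intervals are computed correctly and serve as planning illustrations.** This stands. Nothing in D.1.a commits the final analysis to Wald limits. The issue is the choice of method and the figures it yields, not a slip of arithmetic.
- **The 95% Wald interval performs well at 80%.** Its coverage of 94.6% is essentially nominal. The poor overall coverage belongs to the 85% and 90% intervals. The lower limit at 24/30 is nevertheless too high at all three levels.
- **The decision is unaffected.** This also stands. The cut-off against 50% is 20/30 by every method at the stated level, and at 24/30 every lower limit is at least 61%.

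Two stronger readings are tempting, and the documents do not support them.

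- **That the 95% power was computed at one-sided 2.5% and mislabelled.** The usual normal formula with z = 1.96 does give 95.1%. But 95.0% also follows at the stated one-sided 5% level with the null standard error throughout, and the plan names no formula. That shortcut applies the variance at 50% when the truth is 80%, so it is crude, but it prevents any firm inference about where the figure came from.
- **That the 80% hypothesis in A.3 and the 50% benchmark in D.1.a are conflicting success criteria.** They read as an ordinary alternative and null. A.3 does not say that observing less than 80% means failure.

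**Conclusion.** The point holds for the intervals. As stated, they overstate what 24/30 excludes by 1.8 to 3.0 points relative to Wilson and by 3.4 to 4.3 points relative to exact limits, in the direction that favours the study.

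The power statement is under-specified but errs on the safe side: exact power at the stated level is 97.4%, or 2.4 points above the figure given. Thirty participants are enough for this comparison, and power is still 93.9% at one-sided 2.5%.

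This is a modest correction to reported figures, with no bearing on the design. It assumes independent completion outcomes, a true rate of 80% for the coverage and power figures, and n = 30 as in the plan's own worked numbers. D.1.a words the definition more broadly ("The feasibility of completing the study is defined as the percentage of enrolled participants who complete the study"), so the figures here apply to the weight loss arm only.

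**What to change.** In D.1.a:

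1. Replace the three intervals with Wilson limits (85%: 67.7–88.4; 90%: 65.7–89.3; 95%: 62.7–90.5) or exact limits (66.1–89.9; 64.3–90.9; 61.4–92.3). Name the method and commit to it for the final analysis.
2. Restate the power sentence along these lines: a completion rate of 50% will be ruled out if at least 20 of 30 participants in the weight loss arm complete, using an exact one-sided 5% binomial test (size 4.9%; power 97.4% if the true rate is 80%).

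The cost is wording only, with no change to sample size, visits or data collection. The one downside is that the quoted lower limits become about 2 to 4 points less favourable; the quotable power rises.

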The consent process will be documented in detail including any questions asked by the individuals and the responses provided by research staff. The research staff will date and sign the documentation. In addition, the time the consent process began and ended will also be documented. Prior to the beginning the baseline assessment, participants will be asked once again if they understand the requirements of the study and if they wish to continue. Any subsequent changes to the informed consent process will be submitted to the OSU IRB for approval prior to activation.

Participants assigned to the weight loss group will notify the research study staff of any pre-existing medical conditions, including injuries and recent surgeries, at baseline before they start the weight loss intervention and will inform the research study staff should they experience any medical problems, including injuries, over the course of the weight loss program. Their responses at baseline and throughout the weight loss intervention will be recorded on an Adverse Events Log.

Table 2. Dietary intake and exercise goal.

Dietary budget per day		
Baseline Weight	< 250 lbs	≥250 lbs
Calorie (kcal)	1200-1500	1500-1800
Fat (g)	40-50	50-60
Protein (g)	60-75	75-90
Aerobic exercise (moderate-intensity) per week		
Goal	150-200 min	
Week 1	30-60 min	
Week 2-4	↑ 30 min till reach 150 min	
Week 5-15	>150 min/week	

C.4 Weight Loss Intervention

C.4.a Overview

The proposed weight loss intervention is a 15-week telephone-based, multi-component approach adapted from the Healthy Living and Eating Program (73), which was designed for cancer patients. We will modify the program from the in-person group sessions to a remotely accessible telephone-based intervention to reduce the burden of travel for rural populations and transform the program from a cancer patient's focus to one of a general population with obesity. Participants randomized

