The objective of the behavioral component is to promote increased self-efficacy and social support for lifestyle modifications and gradually facilitate participants' transition toward successful independent self-regulation of a healthy diet and physical activity. The behavioral component focuses upon the acquisition and practice of self-regulatory skills in conjunction with a continuous problem-solving model of behavior change to empower participants to exert greater control over their behavior, cognition, and environment. The behavioral component is designed to: a) increase health knowledge of the benefits of physical activity and dietary modifications; b) enhance self-efficacy and positive outcome expectancies through the promotion of a series of successful experiences in changing exercise and eating behavior; and c) improving self-regulation of exercise and eating behaviors through the use of goal-setting, self-monitoring, stimulus control, cognitive restructuring, and barrier problem-solving strategies. The efficacy of this approach for promoting adoption and maintenance of exercise and dietary behavior change has been demonstrated in prior randomized controlled trials that [name] has served as principal and co-investigator on other studies (106-109).

C.5 Active Control Group

At the beginning of the study, participants randomized to the active control arm will receive education brochures (will be submitted in the first amendment) describing the American Institute for Cancer Research physical activity and dietary guidelines. Participants will be asked to meet the 2018 Physical Activity Guidelines for Americans (150 min/week of moderate-intensity exercise or 75 min/week of vigorous exercise), and increase fruit and vegetable intake, reduce fat intake, reduce sugary drink, increase consumption of whole grain, and increase water intake. An exercise manual with access Online YouTube videos (as another option) will be available as examples for proper exercise form for strength training. We will also encourage them to self-monitor weight, dietary intake, and physical activity through MyFitnessPal or paper log. To achieve the retention and provide motivation and strategies for behavioral change in the active control group, participants will receive a Fitbit and the lifestyle modification manual at the end of the study.

C.6 Covid-19 Safety Protocols and Planning

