also a risk of muscle injury, which may require medical attention, may take several months to heal, and may limit activities of daily living for a period of days, weeks, or months. Participants will be informed that there is an increased risk with starting a physical activity program and be advised of all of the potential risks. Additionally, [name] and research staff with training in exercise physiology and behavioral changes will be directly involved in conducting physical fitness tests and delivering exercise components.

There is a slight risk of breach of confidentiality, but steps are in place to protect participants' personal information. Electronic data will be stored behind a firewall and accessed only by study staff through password-protected computers. Paper-based data will be stored in a locked cabinet within a locked file room.

Collectively, the participants will be assuming no more than minimal risk in completing the assessment protocol and the minimal risk inherent to completing the assessments will be mitigated via stringent pre-test medical screening and during testing supervision.

E.2 Benefits of participation

Participants may gain awareness of healthy eating and physical activity from evidence-based program. Participants in the telephone-based counseling group will receive a physical activity tracker (e.g., Fitbit) at the beginning of the study, and weekly telephone-based weight loss counselling for 15 weeks. Participants in the active control group will also receive a physical activity tracker and lifestyle modification manual at the end of the study. All participants will receive regular body weight, body composition, and blood tests for lipid profiles and inflammatory biomarkers free of charge.

E.3 Adverse events

Adverse events, including any unfavorable and unintended sign (e.g., abnormal laboratory finding or symptom) will be collected as they occur, regardless of whether it is considered related to the weight loss intervention. Musculoskeletal injuries and previously undocumented major medical events incurred during the intervention will be systematically collected on all participants during the study period using standardized forms from our prior work. Patients will have instructions to contact the PI or their primary health providers to discuss and manage any possible side effects. The PI, study coordinator should immediately be contacted in the event such a problem arises.

E.3.a Severity

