The adverse event form will be used by study staff to report injuries or other adverse events reported by participants throughout the study. The patient will be observed and monitored carefully until the condition resolves, stabilizes, or its cause is identified. All adverse events, including laboratory abnormalities, will be followed up according to good medical practices. Information to be recorded includes: 1) specific type of reaction; 2) duration of reaction; 3) severity/grade of reaction according to the NCI Common Terminology Criteria for Adverse Events v4.0 (CTCAE); 4) suspected cause of the reaction (i.e. possibly or probably related to one of the following: study treatment, progression of disease, concurrent medications, concurrent illness, or other factors); 5) changes made in the administration of the study intervention and other actions taken to alleviate the clinical event; and 6) patient's response to medical interventions.

E.3.d Reporting

In accordance with IRB guidelines, serious adverse events will be reported within 10 days of the investigator's or research staff members' learning of the event to OSU IRB. OSU IRB Event Reports should be submitted through BuckIRB at: <http://orpp.osu.edu/irb/buck-IRB/>. Events resulting in temporary or permanent interruption of study activities by the investigator or sponsor to avoid potential harm to subjects should be reported within 48 hours whenever possible.

All events that may represent unanticipated problems involving risks to subjects or others will be promptly reported (as described above), regardless of whether they occur during or after the study, or involve a subject who has withdrawn from or completed study participation. If changes to the research or consent process are proposed as a result of the event, or if additional information will be provided to current and/or past participants, a protocol amendment will be submitted for IRB review.

Related events involving risk but not meeting the prompt reporting requirements will be reported to the IRB in summary form at the time of continuing review.

E.4 Confidentiality

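### The analysis plan carries forward only intervention-related adverse events, with no all-cause summary by arm, although all-cause events are collected

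*Combined protocol and SAP*

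**What the plan says.** **Analysis.** D.1.a defines completion and acceptability and then lists further items to be assessed, beginning "Intervention-related adverse events, satisfactory, and other feasibility assessments". It gives no arm, denominator, time window, summary measure or interval for adverse events. Aim 1 (A.3) uses the same restriction: "we anticipate the minimal occurrence of intervention-related adverse events". D.1.b lists the outcomes to be compared between arms (weight, body composition, activity, diet, lipids, inflammatory markers). Adverse events are not on the list.

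**Collection.** E.3 is wider. Adverse events "will be collected as they occur, regardless of whether it is considered related to the weight loss intervention", and musculoskeletal injuries and new major medical events "will be systematically collected on all participants during the study period using standardized forms from our prior work". C.3.e is narrower. It describes reporting of medical problems only for participants assigned to weight loss: "Their responses at baseline and throughout the weight loss intervention will be recorded on an Adverse Events Log".

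**Attribution.** E.3.c states that "The adverse event form will be used by study staff to report injuries or other adverse events reported by participants", and one item on that form is the "suspected cause of the reaction (i.e. possibly or probably related to one of the following" several listed causes. E.3.b defines four association categories. F.4 has the study team and principal investigators review events. The blinding in C.7 covers the baseline and 15-week outcome assessments; nothing is said about blinding whoever judges relatedness.

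**Control arm.** C.5: "Participants will be asked to meet the 2018 Physical Activity Guidelines for Americans".

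**The concern.** E.1 names muscle soreness and muscle injury as the harms to expect from increased activity. Both arms are asked to be active, so both can have such events. Deciding case by case whether an injury came from the programme cannot show how many injuries coaching adds to advice alone. A randomised control arm can address that, provided events are sought alike in both arms, but D.1 does not use it for harms.

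As written, the safety result is a count that depends on attribution and carries no measure of uncertainty. Attribution is recorded by study staff, apparently unblinded, in a study whose first aim anticipates few related events. D.1.b says the pilot's estimates are to inform a larger trial. A harm figure that cannot be read against the control arm is of little use for that.

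**Working it through.** **1. The sections side by side**

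| Step | Section | Scope |
|---|---|---|
| Collection | E.3 | All-cause; injuries and major events on all participants |
| Log procedure | C.3.e | Weight loss group only |
| Attribution | E.3.b, E.3.c, F.4 | Study staff and team; no blinding or independent assessor described |
| Analysis | D.1.a, Aim 1 | Intervention-related only; no measure or interval |
| Between-arm comparison | D.1.b | Adverse events not listed |
| Monitoring | F.4, Table 5 | Event rates monthly, not limited to related events, not stated to be by arm |

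The restriction enters at the analysis step, not at collection. The plan states no safety rate or threshold, so there is no figure of its own to reproduce. For contrast, the same paragraph of D.1.a gives three confidence intervals for completion.

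**2. What the filter can do (all rates assumed)**

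Let p1 and p2 be the all-cause risks in the weight loss and control arms, and a the share of weight loss arm events called related. The related-only figure is a × p1; the randomised excess is p1 − p2.

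| p1 | p2 | Excess | a = 25% | 50% | 75% | 100% |
|---|---|---|---|---|---|---|
| 30% | 10% | 20 points | 7.5% | 15% | 22.5% | 30% |
| 20% | 10% | 10 points | 5% | 10% | 15% | 20% |
| 20% | 20% | 0 | 5% | 10% | 15% | 20% |

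The figure can fall on either side of the excess. The last two rows give identical related-only figures for different excesses, so that figure alone cannot tell the two situations apart.

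**3. What a by-arm summary would show**

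Newcombe 95% interval for d = p1 − p2, from the Wilson limits (l, u) of each arm:

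- lower = d − √[(p1 − l1)² + (u2 − p2)²]
- upper = d + √[(u1 − p1)² + (p2 − l2)²]

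For 9/30 v 2/20 the Wilson limits are 0.167 to 0.479 and 0.028 to 0.301:

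- lower = 0.200 − √(0.133² + 0.201²) = −0.041
- upper = 0.200 + √(0.179² + 0.072²) = 0.393

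| Weight loss | Control | Difference, points | 95% CI |
|---|---|---|---|
| 9/30 | 2/20 | 20.0 | −4.1 to 39.3 |
| 6/30 | 4/20 | 0.0 | −24.0 to 21.0 |
| 9/30 | 2/15 | 16.7 | −11.3 to 37.0 |

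Power for 30% v 10% (two-sided 5%) is about 37% at 30 v 20 and 29% at 30 v 15. The comparison can only be descriptive.

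**4. Why an interval is needed even for a zero count**

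With 0 events in 30, the exact upper limit is 1 − 0.05^(1/30) = 9.5% (one-sided 95%), or 1 − 0.025^(1/30) = 11.6% (two-sided 95%).

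**5. Whether the data would support the contrast**

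The weight loss arm has weekly calls (C.4.a, C.4.d) and the log in C.3.e. Controls receive brochures at the start (C.5), and the scheduled assessments are at baseline and 15 weeks (C.7). More contact can bring more events to light, so a plain risk difference could be biased against the programme.

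**The case against.** The strongest reply is that this is a small pilot with completion and attendance as its hypotheses, that safety is a side statement with no threshold, and that adverse events are handled under monitoring. Several parts of that stand, and they rule out stronger readings that a reader might infer.

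- *That related events are the only safety information the study will look at.* Not supported. Table 5 has monthly review of adverse event rates, and F.4 has all events reviewed by the team and reported under IRB policy. The restriction is confined to Aim 1 and D.1. Monitoring is not a planned result, however, and is not described by arm.
- *That the planned count covers the weight loss arm alone.* D.1.a does not say so; the limit to that group belongs to the acceptability definition just before it.
- *That injuries blamed on work or an old problem drop out, so harm will be understated.* E.3.b points the other way: a timely event of a known pattern with a possible alternative cause is rated probably related, and an unrelated rating needs evidence of another definite cause. Under-attribution cannot be presumed, and over-attribution is equally open.
- *That the assessor is known to be unblinded.* The documents name no assessor. Team attribution is a fair reading of E.3.b, E.3.c and F.4, but what can be said is that no blinding is described.
- *That the fix is a matter of analysis wording.* It is not, because C.3.e and E.3 describe different ascertainment.

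What the reply does not answer is why events collected without regard to relatedness should reach the analysis only after a relatedness filter, with no interval.

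**Conclusion.** The concern holds for the analysis plan. D.1 carries forward intervention-related events only and plans no all-cause summary by arm, between-arm contrast or interval. The resulting figure depends on attribution and can lie above or below the excess that randomisation would estimate.

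The direction and size of any error are unknown. Every event rate and attribution share above is an assumption, used only to show that both directions are possible. Because controls are asked to exercise too, a by-arm contrast would estimate the programme's added risk over advice, not over no exercise. It would be imprecise, and trustworthy only if events are sought in the same way in both arms. The plan should be changed, as a matter of reporting; the point does not bear on the completion or acceptability analyses.

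**What to change.** 1. **D.1.a.** Replace the safety item with, for example: *For each arm we will report the number and percentage of participants with at least one adverse event of any cause, at least one musculoskeletal injury and at least one serious adverse event, with exact 95% confidence intervals, and the between-arm risk difference with a 95% (Newcombe) interval. No test will be made. Events judged intervention-related will be shown as a subset.*
2. **Aim 1.** Read the expectation of few related events alongside these figures and their upper limits.
3. **C.3.e and E.3.** Reconcile the two so that the standardised form is put to both arms in the same way, for example at the existing week-15 visit. Base the between-arm contrast on that common enquiry, and report separately the events found only through the weekly calls.
4. **E.3.c.** State who judges relatedness and whether that person knows the arm.

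Cost: a few sentences, one table and one added enquiry for controls at a visit already planned. The intervals will be wide at 30 v 15 to 20, and some difference in ascertainment will remain because only one arm is called weekly.
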